### **Project Plan**

We will collect pilot data and develop pilot research in order to develop into a federally funded proposal. A unique aim of this study is to test hypotheses about alterations in specific neurocognitive processes as potential contributors to cognitive rigidity which is the opposite of cognitive flexibility. Alterations in behavioral flexibility will be assessed using probabilistic reversal learning (PRL) paradigms. In PRL, a subject must learn to choose between two stimuli. The “correct” choice is reinforced on a majority of trials (80%), and the other choice reinforced on 20% of trials. Subsequently, the contingencies are reversed between choices. Our recent work found that individuals with autism are impaired on PRL. We also showed that reversal learning errors are related to clinical measures of repetitive behaviors. Furthermore, individuals with autism also exhibit social deficits. Thus, it is critical to expand on the center’s focus to build a more comprehensive understanding of autism, as well as to develop the most efficacious and rationale treatments.

As an essential first step to achieving these longer-term goals, we have the following specific aims. Our goal is to recruit 60 individuals with autism who have already demonstrated an ability to perform the reversal learning paradigm.

**Aim 1:** Examine whether acute IN-OT treatment vs. placebo improves social cognition and replicates other ASD studies to date.

**Aim 2:** Determine whether acute IN-OT treatment vs. placebo improves cognitive flexibility as a novel drug target or future treatment outcome measure.

Preliminary human data with this Protocol: Preliminary PRL and genetic data has been collected at the University of Illinois at Chicago (UIC) on over 300 individuals. Also at UIC, the same protocol for the Single Dose Intranasal Oxytocin (IN-OT) Versus Placebo in Autism study was completed while [name], the PI, moved to the University of MN. Eighteen subjects safely completed this protocol between May and October of 2012 (UIC IRB Protocol #: 2011-1082; Title: Single Dose Intranasal Oxytocin (IN-OT) Versus Placebo in Autism: Examining Cognitive Effects). Subjects tolerated the drug and protocol well and all safety data was sent to the FDA, IND #114259 (UIC IND).

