**Task Data:** Rigidity was examined using computer paradigms that were designed to closely approximate 2-choice T-maze and 4-arm radial maze tasks, which are widely used in studies of reversal learning in rodents (13, 21). It was found that children with ASD demonstrate impairments in flexibly shifting from preferred behavioral patterns to new adaptive response strategies. The ASD group required more trials to successfully complete their reversal phase ( $t(79)=-2.08$ ,  $p=0.04$ ) and made significantly more regressive errors ( $p=0.019$ ). In addition, the number of regressive errors were correlated with total score on the RBS-R ( $p=0.003$ ) (Figure 1).

**Physiology Data:** Autonomic Nervous System (ANS) measures as physiological indicators of emotional state were also studied. Preliminary results of reactivity to stressful challenges show that children with ASD have a higher heart rate (HR;  $F(1, 51)=5.53$ ,  $p=0.023$ ) and lower respiratory sinus arrhythmia (RSA;  $F(1, 51)=4.25$ ,  $p=0.045$ ) than controls, indicating a tendency for decreased flexibility during novel or stressful situations. Only one study has examined ANS with IN-OT (20 IU) in 40 adults and reported that it increased RSA but less in individuals who reported high levels of loneliness (22). Given that children with ASD may be less able to self-report emotional state information, ANS measures may also help us assess baseline anxiety or social aloofness and see how they correlate to response outcomes with intranasal challenge (IN-C).

**Eye Gaze Tracking:** During facial/video recognitional task the movement of the eyes will be tracked. This measurement allows us to correlate the gaze area and time spent gazing with the subject's ability to interpret emotions. An earlier study showed that children with less severe ASD symptoms and ASD children with increased gaze to the eye region were able to more accurately recognize emotions (23).

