Individuals will come to the lab to participate in a randomized, placebo-controlled, crossover single dose challenge study to examine the effects of IN-OT challenge on social as well as cognitive flexibility outcomes. After collecting baseline data, the IN-C will be given on two visits separated by approximately two weeks. Vital signs will be taken and subjects will be monitored for adverse events (AEs). Blood, urine and saliva will be collected before and after IN-C at both study visits. We will measure plasma, urine and saliva for levels of hormones, metabolites and peptides related to or interacting with OT. Additionally DNA will be extracted from the blood samples to study genes related to OT and ASD if the subject consents to genetic analysis. Subject assessments will be done by an evaluator who is blinded to content of IN-C. All ASD studies published to date report 24-48 IU of OT to be well-tolerated and intranasal-placebo>intranasal-oxytocin side effects. Subjects will be monitored for side effects. Safety evaluations will be done by a blinded MD investigator.

OT acquisition & dosing schedule: IN-OT is currently not manufactured in the U.S. but has been obtained from Victoria Apotheke (Zurich, Switzerland). They are also providing the drug for [name] current 12-week intranasal trial in autism. We will use a weight-adjusted dose based on the 40 IU dose, block design based on 0.6 IU/kg/dose. The randomized IN-OT versus IN-placebo session will be separated by approximately two weeks. Placebo will be identical to the OT formulation with the exception of the active compound. It is prepared under aseptic conditions with carrier ingredients identical to OT nasal spray.

**Aim 1: Social tasks:** ASD subjects exhibit impairments in processing both social visual and auditory cues. The purpose of Aim 1 is to determine whether a single dose of IN-OT reduces deficits in processing social and auditory recognition tasks, especially, tasks that

require assessment of an emotional state to make a decision. The data collected will indicate the degree of impairment in the subject's ability to recognize social visual and auditory cues.

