## **Design**

The treatment intervention will be a double-blind placebo-controlled cross-over challenge study of IN-OT versus placebo separated by a drug-free period of approximately two weeks. Enrollment will be up to 30 subjects. The primary outcome measuring changes in cognitive flexibility will include regressive errors on our PRL task. In addition, to examine changes in social cognition RMET will be utilized. We will test cognitive flexibility along with social tasks via computer. One of the goals of this initial study is to choose the best outcome measures for future trials. Additionally, the standardized clinical measurements, Repetitive Behavior Scale-Revised (RBS-R), State-Trait Anxiety Inventory for Children (STAI; or Adults based on age and developmental abilities) and ABC-CV stereotypy, will be included.

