**Anticipated results & interpretation:** This study will be essential in allowing us to examine mechanisms of OT modulation of social or rigid behaviors in ASD. Our primary analyses will focus on IN-OT versus placebo differences in RMET for social perception and the PRL task as a measure of rigidity. Additional social cognition and rigidity tasks will be explored to assess appropriate measures for future studies investigating mechanism of OT change or treatment outcomes. Our ultimate goal is to see if IN-OT can be used to augment social or behavioral learning therapies and compare the risk and benefits of paired IN-OT treatment versus chronic administration (currently being conducted at UMN) in targeting specific subdomains within ASD across development.

**Sample composition:** Sample heterogeneity, for instance with respect to symptom severity, might affect treatment response. Restricting the sample to prescreened subjects who can perform cognitive tasks reduces heterogeneity.

**Concomitant medication and treatments:** Although we acknowledge that concomitant medications, or other types of intervention, may potentially bias study results, participants will be allowed to stay on concomitant medications (except antipsychotic drugs) and non-pharmacologic treatments, provided that no changes are made within 3 months prior to baseline and that no changes are made during the study. Information from the treatment history form can be used in ad hoc analyses to highlight potential confounding factors.

**Intervention attrition and missing data:** An intent-to-treat analysis will be used including every randomized participant who has baseline data. We will make every effort to minimize dropouts in order to preserve the integrity of the study; however, we recognize that missing data in pre-post designs are inevitable. For missing data, multiple imputation methods will be considered. Logistic regression will be used to obtain adjusted estimates of treatment effects for the primary measures. We will document reasons for dropouts and we will compare the characteristics of the subjects who drop out to those who complete.

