**Recording, Evaluating and Reporting Adverse Events and Serious Adverse Events**

The investigator will attempt to establish a diagnosis of the event on the basis of signs, symptoms, or other clinical information. In such cases, the diagnosis, not the individual signs or symptoms, should be documented as the AE or SAE. Any adverse events--whether due to assessment, imaging, medication or other aspects of any project--will be reported to the principal investigator or the co-investigator of each study. Unanticipated (non-serious) events will be reported to the IRB within 30 days of the principal investigator becoming aware of the event, via submission of an Adverse Event Report. Adverse events will be documented and reviewed by the principal investigator within 24 hours of the principal investigator becoming aware of the event. Serious events will be reported to the IRB and FDA within 48 hours of the principal investigator becoming aware

of the event. Notification will be by phone, email, or fax. A completed Adverse Event Report will be submitted within 10 days of initial IRB notification. All deaths will be reported to the IRB and FDA within 48 hours of the principal investigator becoming aware of the event. All adverse events will be compiled, and reported in summary form to the IRB, on an annual basis and at the conclusion of the study.

Dosage: The question of appropriate dosage remains. The majority of studies of IN-OT in ASD have used 24 IU per dose to document behavioral and biological (fMRI) effects (2). The range reported across neuropsychiatric disorders including ASD is 18-48 IU per dose (35). At this point, we plan to use a weight-adjusted dose based on the 40 IU dose, i.e. 0.6 IU/kg/dose with the assistance of University of Minnesota Medical Center, Fairview, Investigational Drug Services Pharmacy. We have had to make such a weight adjustment for our current international multidose study in adolescents with ASD. In the case that regulatory agencies raise an issue with the chosen dosage, we will follow their guidelines. Participants will be asked to take the dose of IN-OT or placebo in the form of intranasal spray and then begin the tasks.

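### Logistic regression is the only model named for the primary measures, but PRL errors are a count, RMET has no binary definition, and no within-person model is given for the crossover

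*Combined protocol and SAP*

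**What the plan says.** The paragraph on intervention attrition and missing data contains the only sentence that names a model for treatment effects: "Logistic regression will be used to obtain adjusted estimates of treatment effects for the primary measures". It does not list the adjustment covariates. The same paragraph says multiple imputation will be considered, but that is not a treatment-effect model.

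The primary contrast is set out under anticipated results and interpretation: "Our primary analyses will focus on IN-OT versus placebo differences in RMET for social perception and the PRL task as a measure of rigidity". The Design section defines the rigidity outcome: "The primary outcome measuring changes in cognitive flexibility will include regressive errors on our PRL task". The Task Data paragraph treats this quantity as a number of errors: "the number of regressive errors were correlated with total score on the RBS-R". RMET is listed in the Design section and Table 1 as the primary social outcome, with no scoring rule, cut-off or responder definition.

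On design: "The treatment intervention will be a double-blind placebo-controlled cross-over challenge study of IN-OT versus placebo". Table 2 lists study drug or placebo, and the behavioral outcomes, at both study visits.

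**The concern.** Logistic regression needs a binary response. One primary measure is a count of errors, and the other is a task whose outcome is never defined as binary. To apply the stated model, the analyst must either split each score at a cut-off the plan does not give, or break the task into single responses in a layout the plan does not describe.

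The design is also paired. A crossover gains its precision from comparing each person with themselves, and the plan has no term that does this.

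The two obvious ways of filling the gap with ordinary logistic regression go wrong differently:

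- **Splitting the score and treating sessions as unrelated** discards information and loses power.
- **Pooling all items as independent rows** can understate the standard error and raise the false-positive rate, because a person's performance may shift between sessions.

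One stated goal of the study is to choose outcome measures for later trials. A weak or miscalibrated test could wrongly drop or wrongly promote RMET or PRL.

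**Working it through.** **1. Text check.** The t, F and r statistics under Task Data, Physiology Data and Figure 1 are preliminary results, not planned analyses. No section names a paired test, a mixed model, generalized estimating equations, a conditional logistic model, or a participant, period or sequence term. No section defines a binary form of RMET or PRL.

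**2. No planned figure to reproduce.** The documents give no alpha, power, effect size, SD, within-person correlation, item count or session variation. Sample size is up to 30 in the Design section and 60 in the Project Plan. Everything below is illustration under assumptions: two-sided 5% test, normal scores with SD 1, true shift 0.5 SD, within-person correlation ρ of 0.3 to 0.8, no period effect and no dropout.

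**3. Paired analysis, hand check (n = 30, ρ = 0.5).** The standard error of the mean difference is √(2(1−ρ)/n) = √(1/30) = 0.183. The ratio is 0.5/0.183 = 2.74. Normal-approximation power is Φ(2.74 − 1.96) = Φ(0.78), about 78%. The paired t test gives 75% by simulation.

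**4. Ordinary logistic on a split score, hand check (n = 30 per condition, cut midway between the condition means).** The proportions above the cut are Φ(0.25) = 0.599 and 0.401. The log odds ratio is 2 × ln(0.599/0.401) = 0.80. Its standard error is √(2/(30 × 0.599 × 0.401)) = 0.527. The ratio is 1.52, and power is Φ(1.52 − 1.96), about 33%. Simulation with this cut gives 33%, 31% and 29% at ρ = 0.3, 0.5 and 0.7.

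**5. Simulation, cut at the pooled median (20,000 trials per setting).** Figures are power, in the order ρ = 0.3 / 0.5 / 0.7 / 0.8. The binary paired test is the McNemar score test on the same split.

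| n | Paired t on the score | Ordinary logistic on the split | McNemar on the split |
|---|---|---|---|
| 30 | 61 / 75 / 93 / 99% | 39 / 37 / 36 / 35% | 38 / 42 / 52 / 62% |
| 60 | about 90 / 97 / >99 / >99% | 57 / 58 / 59 / 60% | 68 / 75 / 85 / 91% |

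At n = 30 the ordinary logistic test has type I error of about 4%, 3%, 1% and 0.5%, so it becomes more conservative as the correlation rises. McNemar stays well below the paired t, which shows that the split itself costs power. Comparing steps 4 and 5, moving the cut alone changes logistic power by about 6 to 7 points.

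**6. Pooled items as independent rows, no true effect.** Assumed: 20 to 36 items, mean 0.4 logits, participant SD 0.8 logits, and a session-to-session SD within person.

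| Session SD (logits) | Type I error, pooled logistic |
|---|---|
| 0 | about 4% |
| 0.2 | 5–7% |
| 0.3 | 7–11% |
| 0.5 | 14–21% |
| 0.8 | 25–36% |

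The rates are nearly the same at n = 30 and n = 60, so a larger sample does not cure the inflation. A paired t test on the same data stays at about 5%. As a check, the ratio of true to modelled standard error at n = 30 runs from 0.94 (session SD 0) to 2.14 (36 items, session SD 0.8). Then 2Φ(−1.96/0.94) is about 4% and 2Φ(−1.96/2.14) is about 36%, which agrees with the ends of the table.

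**The case against.** - **The plan is silent on pairing; it does not say pairing will be ignored.** This stands. The losses describe the plainest reading of the text, not a certainty.
- **Logistic regression could be valid.** PRL consists of repeated two-choice trials, so trial-level or item-level responses could be fitted with a clustered or conditional logistic model. This is true in principle, but the plan states neither that unit of analysis nor a participant effect.
- **The magnitudes rest on assumptions.** This also stands. The higher type I error rates need session SDs that no document supports. The two harms belong to different layouts and must not be added together. Ignoring pairing is not always what costs power: at n = 30 and ρ = 0.3, McNemar (38%) does no better than ordinary logistic (39%), so nearly all the loss there comes from the split. Exact McNemar on that split is lower still, at about 27% to 45% across the range of ρ.
- **The sentence sits under missing data and may concern dropout.** Its words refer to treatment effects on the primary measures. If dropout was meant, the plan has no primary model at all.
- **This is a pilot.** That softens the consequences, but the protocol still names primary analyses, and it uses the study to select outcome measures.

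**Conclusion.** The concern holds. The one named model does not fit a PRL error count or an RMET outcome with no binary definition, and no within-person comparison is specified for a two-session crossover. That conclusion rests on the text alone and affects both primary outcomes.

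The size is illustrative. At a 0.5 SD effect and correlations of 0.3 to 0.8, splitting the score and ignoring pairing takes power at 30 participants from 61–99% down to 35–39%. At 60 participants it falls from about 90% or more to 57–60%. If items are pooled as independent rows, type I error stays near nominal when sessions vary little, but reaches 14–36% at session SDs of 0.5 to 0.8 logits. Which of these would apply, if either, depends on choices the plan leaves open, so it should be corrected before the data are analysed.

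**What to change.** Replace the logistic regression sentence with a model for each measure, for example:

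> Each primary measure will be compared within person between IN-OT and placebo. The RMET total score will be analysed with a linear mixed model with treatment and period as fixed effects and participant as a random effect, reporting the IN-OT minus placebo mean difference with its 95% confidence interval. PRL regressive errors will be analysed by the same within-person comparison, with a rank-based or count-model sensitivity analysis.

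Other suitable within-person models would also serve. What matters is that the score, the model and the participant effect are fixed in advance. List the covariates behind the promised adjustment, and say how participants with one visit are handled and how multiple imputation fits with the model. If a binary endpoint was intended, define its cut-off now and name a conditional or clustered logistic model. If logistic regression was meant only for modelling dropout, say so.

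Two side clarifications are worth making in the same edit, though the conclusion does not depend on them:

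- **Baseline.** State whether the baseline data required for the analysis set include pre-dose RMET or PRL values. The Methods section says "After collecting baseline data, the IN-C will be given on two visits separated by approximately two weeks". The Dosage paragraph has participants "take the dose of IN-OT or placebo in the form of intranasal spray and then begin the tasks". Table 2 does not show task timing within a visit.
- **Sample size.** Reconcile the Project Plan ("Our goal is to recruit 60 individuals with autism who have already demonstrated an ability to perform the reversal learning paradigm") with the limit of 30 in the Design section.

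The cost is wording in the analysis paragraph, plus these clarifications. No new data, visits or participants are needed.

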### **Data management & Sources of Material**

The sources of research material obtained from each participant will be in the form of information gathered specifically for research purposes. This will include data from diagnostic testing, cognitive and neuropsychological data, clinician and evaluator ratings (e.g. safety measures), and blood, urine and saliva samples. Additionally, DNA will be extracted from the blood samples to study genes related to OT and ASD if the participant consents to the collection. Data and records will be rigorously protected. To protect participants' confidentiality, only authorized persons will have the right to review research records. Confidentiality of those records will be protected to the extent permitted by law. For all data, the identity of study participants will be kept confidential, such that all participants will be assigned a unique identifying number under which all obtained information will be coded. Research records will be de-identified or be kept in secure, encrypted, password-protected databases and will be accessible only by key study personnel and will not be released without the subject's consent unless required by law (e.g. suspected abuse) or a court order. All biological samples will be labeled using unique numerical identifiers that can only be linked to subject identity by a key stored in the locked archive. When the results of this research are published or presented at scientific meetings, the identity of subjects will not be disclosed.

### **Potential Risks & Safety Monitoring and Assessment**

This study may present greater than minimal risk to subjects. For the screening, behavioral testing and evaluations, and blood draw, the risks to the subjects are minimal, sometimes involving test anxiety, apprehension and fatigue, discomfort, and breach of confidentiality. For the administration of IN-OT, the risk to subjects may be greater than minimal. We will take numerous safety precautions to ensure the safety and well-being of participants.

**Intranasal oxytocin:** For the OT component of the study, the primary risks are related to potential side effects. Side effects of IN-OT may include nasal irritation, runny nose, or tearing of the eyes. Additional rare side effects reported in single cases and of unknown relationship with the medication include allergic dermatitis, unusual bleeding, difficulty passing urine, sudden weight gain, convulsions, nausea, drowsiness, headache and rarely confusion, anxiety, sad mood, fast or irregular heartbeat (palpitations) and unusual swelling. Large doses of intravenous OT decrease both systolic and diastolic blood pressure through a transient relaxation of vascular smooth muscle. Any OT-induced decrease in blood pressure is followed by a mild but sustained increase. IN-OT, which will be used in the present study, has not been found to substantially affect blood pressure.

**Medication:** Exogenous OT is metabolized by chymotrypsin in the GI tract and thus cannot be administered orally. It can be administered in either an intravenous or an

intranasal form. Currently, the only form of OT that is available in the US is the intravenous form. Although this formulation has been found to produce positive effects on social cognition in ASD (11), it is invasive to administer and the extent to which this formulation crosses the blood-brain barrier (BBB) is unknown. One alternative is IN-OT, which is absorbed through the highly permeable nasal mucosa and has been shown to pass the BBB (25). IN-OT remains on the market outside the US and Canada (e.g., Syntocinon®, NOVARTIS, Switzerland). The applicant currently holds INDs for studying oxytocin in ASD children and adults (IND#109833; #114259). The effect on smooth muscle after intranasal administration of 10-20 IU lasts approximately 20 min, which reflects its duration of action in the periphery and outside the BBB (26). Mean CSF concentrations of peptides like OT begin to rise within 10 minutes of intranasal administration and last for up to 90 minutes after intranasal administration (25). OT is distributed throughout the extracellular fluid and most is rapidly destroyed in the liver and kidneys. Only small amounts are excreted unchanged in the urine. IN-OT will be accessed in the same ways as our chronic OT treatment studies, and will be obtained the same way for this project.

